#### 9.4.5 BASELINE DESCRIPTIVE STATISTICS

Baseline characteristics, including demographic characteristics, medical history, patient-reported outcomes and physical measurements will be summarized using descriptive statistics.

---

#### 9.4.6 TABULATION OF INDIVIDUAL PARTICIPANT DATA

Listings of adverse events may be produced.

---

#### 9.4.7 EXPLORATORY ANALYSES

Visual severity of nasal congestion and turbinate hypertrophy will be evaluated for each side of the nasal cavity separately. Screening, 1- and 3-Month timepoint scores will be cross-tabulated, and the proportion with improvement will be calculated.

---

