## 6 STUDY TREATMENT

### 6.1 STUDY TREATMENT ADMINISTRATION

All subjects will receive bilateral cryoablation treatment with the ClariFix device per Instructions for Use (IFU) (See Appendix I).

Each side of the nasal cavity will be treated in two locations (see Figure 3): (a) middle meatus and (b) inferior meatus. Each location will receive approximately thirty (30) seconds of cryoablation treatment.

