#### 8.3.1 PHYSICAL NASAL EXAM

A physical nasal evaluation of the treatment area and nasal cavity will be performed by a licensed clinician via endoscope at the Screening (Visit 1), 1-Week (Visit 4 due to AE occurrence or monitoring), 1-Month (Visit 5) and 3-Month (Visit 6).

**IMPORTANT:** Except for 1-Week (Visit 4), if applicable, subjects are not to be decongested prior to the Physical Nasal Exam.

Prior to decongestant, bilateral endoscopic videos or images are to be collected capturing the head of the inferior and middle turbinates (see Section 8.3.3).

The clinician will assess each side of the nasal cavity for hypertrophy of the middle and inferior turbinates and congestion using a 0 to 3 scale (0=None, 1=Mild, 2=Moderate, or 3=Severe).

After decongestant, a second bilateral endoscopic videos or images are to be collected capturing the head of the inferior and middle turbinates.

At Visit 4 (if applicable), Visit 5 and Visit 6, the clinician will assess each treatment area (left middle meatus, left inferior meatus, right middle meatus and right inferior meatus) for bleeding, crusting, and swelling using the same scale of 0 to 3.

An endoscopic exam may be completed at an Unscheduled Visit at the discretion of the Investigator, in the event of a study-related adverse event.

---

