## 9.4 STATISTICAL ANALYSES

### 9.4.1 GENERAL APPROACH

All statistical analyses will be performed using a two-sided hypothesis test at the overall 5% level of significance. P-values will be rounded to three decimal places. If a p-value is less than 0.001 it will be reported as "< 0.001." If a p-value is greater than 0.999 it will be reported as "> 0.999." No adjustments for multiplicity are planned.

Continuous data will be summarized using descriptive statistics: n, mean, standard deviation or standard error, median, minimum and maximum. The decision to use either standard deviation or standard error will be based upon the objective of the presentation: standard deviation will be used when the interest is the natural variability of the data; standard error will be used when comparing two or more means. Continuous variables that are recorded using approximate values (e.g., < or >) will be replaced by the closest exact value for the calculation of summary statistics.

Categorical variables will be summarized using frequency counts and percentages.

For ordinal-scaled variables, a combination of the above may be employed as appropriate: frequency and percentage of observations within a category and means and standard deviations of the scores of the categories.

For categorical and ordinal variables, percentages will be calculated based on non- missing data.

All analyses will be based on available data; no imputation for missing data will be conducted.

Baseline is defined as the last measurement for the outcome of interest obtained before the exposure to the study device.

Duration variables will be calculated using the general formula: [(end date – start date) +1]

Within-subject changes will be calculated as visit value minus baseline value such that a negative change reflects a decrease and a positive change signifies an increase. No judgment (“better” or “worse”) is associated with the sign of the change, only direction. The Wilcoxon Signed Rank test will be used to test the null hypothesis that the mean (or median) within-subject change is equal to zero.

---

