7.2.3 Quantitative nasal endoscopy scores

Endoscopic nasal examinations (before and after decongestant administration) will be performed at baseline and at the 30-day and 90-day follow-up visits. Photos will be taken of the middle and inferior turbinates (before and after decongestant). After deidentification and randomization, an independent physician, blinded to the participant and study visit, will review and grade each photo for 3 findings (inferior turbinate hypertrophy, middle turbinate hypertrophy, and nasal congestion). Each finding will be rated on a scale from 0 (none) to 3 (severe).³ Predecongestant and postdecongestant scores for each finding will be summarized using counts and percentages at baseline and the at the 30-day and 90-day visits.

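### The endoscopic improvement rate in Protocol 9.4.7 has no defined denominator, and SAP 7.2.3 plans no paired change for an endpoint that SAP 3.1.1 defines as a change

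*Protocol*

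**What the plan says.** - **Unit.** Protocol 9.4.7 states that congestion and turbinate hypertrophy "will be evaluated for each side of the nasal cavity separately".
- **Summary.** The same section continues: "Screening, 1- and 3-Month timepoint scores will be cross-tabulated, and the proportion with improvement will be calculated". It does not say what counts as improvement or which sides form the denominator.
- **General rule.** For categorical and ordinal variables, Protocol 9.4.1 says "percentages will be calculated based on non- missing data".
- **Scale.** Protocol 8.3.1 has the clinician grade each side "using a 0 to 3 scale (0=None, 1=Mild, 2=Moderate, or 3=Severe"). SAP 7.2.3 uses the same 0 to 3 range for the blinded reading of photos.
- **Eligibility.** Protocol 5.1 requires patient-reported rhinorrhea and congestion on the rTNSS. Neither 5.1 nor 5.2 sets a minimum endoscopic grade.
- **Paired analysis in the Protocol.** Section 9.4.3 lists physician-assessed congestion and turbinate hypertrophy as secondary endpoints and refers them to 9.4.2, which plans changes from baseline and Wilcoxon signed rank tests. The unit, side or participant, is not stated.
- **SAP.** Section 3.1.1 lists the change in these grades at 30 and 90 days as a secondary endpoint. Section 7.2.3 then plans only this: "Predecongestant and postdecongestant scores for each finding will be summarized using counts and percentages", at each of the three visits. It mentions no change, no improvement rate and no left/right split.

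**The concern.** There are two linked gaps.

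First, the improvement rate in 9.4.7 can be read in more than one way. If every graded side counts, sides that looked normal at Screening enter the denominator but can never enter the numerator. The rate then depends partly on how many sides started at 0, and that share may differ between congestion, middle turbinate and inferior turbinate. Rates for the three findings would not be directly comparable. If the denominator is chosen after the data are seen, the result could move by many points in a study of 30.

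Second, the SAP removes the analysis that would show who changed. Separate grade distributions at baseline, 30 and 90 days do not link a participant's grade at one visit to the same participant's grade at the next. As written, SAP 7.2.3 does not estimate the endpoint that SAP 3.1.1 names.

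**Working it through.** The plan gives no target rate, no expected share of grade-0 sides and no between-side correlation, so there is no stated figure to reproduce. The values of f, p and r below are assumptions, shown over ranges.

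**1. Cap from the floor**

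Inputs: scale floor of 0 (Protocol 8.3.1, SAP 7.2.3); denominator of all non-missing sides (Protocol 9.4.1); f = share of sides graded 0 at Screening; p = improvement rate among sides graded 1 to 3.

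Highest possible rate = 1 − f. Reported rate = p × (1 − f). With p = 60%:

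| f | Cap | Reported rate |
|---|---|---|
| 10% | 90% | 0.6 × 0.9 = 54% |
| 30% | 70% | 0.6 × 0.7 = 42% |
| 60% | 40% | 0.6 × 0.4 = 24% |

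In whole counts with 30 sides and p near 80%: at f = 10%, 22/30 = 73% against 22/27 = 81%; at f = 30%, 17/30 = 57% against 17/21 = 81%; at f = 50%, 12/30 = 40% against 12/15 = 80%.

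**2. What restricting the denominator does to the interval**

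Clopper-Pearson 95% intervals at f = 30%:
- p near 0.5: 10/30 gives 0.173 to 0.528 (width 0.355); 10/21 gives 0.257 to 0.702 (width 0.445).
- p near 0.8: 17/30 gives 0.374 to 0.745 (width 0.371); 17/21 gives 0.581 to 0.946 (width 0.365).

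Setting aside the zeros makes the rate interpretable. It does not make it reliably more precise.

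**3. What per-visit tables can and cannot show**

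As an illustration, suppose half of 30 participants are at grade 1 and half at grade 2, both at baseline and at 30 days (15 and 15 each time). Those two tables fit nobody changing, 0/30 improved. They fit equally well every participant switching grade: 15/30 = 50% improved and 15/30 = 50% worsened. The SAP 7.2.3 tables cannot tell these apart.

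**4. Combining the two sides**

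The mean of left and right has variance (1 + r)/2 times that of one side, where r is the between-side correlation and the two variances are taken as equal. For r = 0.2, 0.5 and 0.8 the ratio is 0.60, 0.75 and 0.90. Its square root is 0.775, 0.866 and 0.949, so intervals are about 23%, 13% and 5% narrower. This applies to a mean score, not to a proportion improved.

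**The case against.** The case for leaving the text alone has real substance.

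- **Section 9.4.7 does not say that grade-0 sides are kept.** A reader might infer that it does. The section is silent, and inclusion follows only from the default in 9.4.1. The defect is an undefined denominator, not a stated wrong one.
- **The planned cross-tabulation would show the Screening grade-0 row.** A reader could recompute the rate from it. That stands for the Protocol, but SAP 7.2.3 does not carry the cross-tabulation forward.
- **The Protocol already plans paired changes with signed rank tests** in 9.4.2 and 9.4.3. That also stands, and it makes the omission in SAP 7.2.3 the clearer of the two gaps.
- **Reporting by side is defensible.** It is tempting to argue that, because "All subjects will receive bilateral cryoablation treatment with the ClariFix device", the two sides are interchangeable and splitting them only wastes precision. The documents do not support that. SAP 4.1 permits a second freeze at each location at the physician's discretion, and SAP section 6 records freeze number and duration by side, so exposure may differ. The precision gain depends on an unknown r and is small when r is high.
- **Restricting to participants who can improve has its own bias.** In an uncontrolled study with imperfect grading, leaving out those at the floor favours apparent improvement through regression to the mean. This stands, and is why the all-participant rate should appear alongside.

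**Conclusion.** The point holds as a gap in definition plus a mismatch between the SAP's endpoint and its analysis. If all non-missing sides count, the cap at 1 − f is arithmetic. Its size depends on f, which no document gives: from 6 points (60% to 54%) at f = 10% to 36 points (60% to 24%) at f = 60%.

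Two stronger readings should be avoided. One is that the reported rate would mainly reflect how many noses looked normal at entry; at f = 10% it plainly would not. The other is that the cap is worst for post-decongestant images. That may be a reasonable expectation, but nothing in the documents establishes it.

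The rate in 9.4.7 is exploratory, with no test, threshold or decision attached, in a feasibility study of 30 without a power calculation. Severity is minor. It is still worth correcting, because the same grades form a secondary endpoint in the synopsis and in SAP 3.1.1, and the SAP as written does not estimate the change it names.

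**What to change.** In SAP 7.2.3 and Protocol 9.4.7:

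1. For each finding and decongestant state, form one participant-level score, left plus right, range 0 to 6.
2. Report its paired change from Screening at 30 and 90 days.
3. Define improvement as a fall of at least 1. Report the proportion improved among participants with a Screening score of at least 1, beside the proportion among all participants and the number scoring 0 at Screening.
4. Keep the left and right cross-tabulations as supporting tables.

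The cost is wording in two sections, with no new data. The downsides should be stated in the report: the improvement denominator is smaller and varies by finding, its interval may be wider, and it selects participants with room to improve. Summing also lets worsening on one side offset improvement on the other, which the side tables will show.

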## 10 SUPPORTING DOCUMENTATION AND OPERATIONAL CONSIDERATIONS

---

### 10.1 REGULATORY, ETHICAL, AND STUDY OVERSIGHT CONSIDERATIONS

---

#### 10.1.1 INFORMED CONSENT PROCESS

---

##### 10.1.1.1 CONSENT DOCUMENTS PROVIDED TO PARTICIPANTS

An Informed Consent Form (ICF) describing in detail the study treatment and study device, study procedures, and risks are to be given to each participant and written documentation of informed consent is required prior to initiating any study-related activities.

---

##### 10.1.1.2 CONSENT PROCEDURES AND DOCUMENTATION

Informed consent is a process that is initiated prior to the individual's agreeing to participate in the study and continues throughout the individual's study participation. Consent forms will be Institutional Review Board (IRB)-approved and the participant will be asked to read and review the document. The investigator, or qualified designee, will explain the research study to the participant and answer any questions that may arise. A verbal explanation will be provided in terms suited to the participant's comprehension of the purposes, procedures, and potential risks of the study and of their rights as research participants. Participants will have the opportunity to carefully review the written consent form and ask questions prior to signing. The participants should have the opportunity to discuss the study with their family or think about it prior to agreeing to participate. The participant will sign the informed consent document prior to any procedures being done specifically for the study. Participants must be informed that participation is voluntary and that they may withdraw from the study at any time, without prejudice. A copy of the informed consent document will be given to the participants for their records. The informed consent process will be conducted and documented in the source document (including the date), and the form signed, before the participant undergoes any study-specific procedures. The rights and welfare of the participants will be protected by emphasizing to them that the quality of their medical care will not be adversely affected if they decline to participate in this study.

---

#### 10.1.2 STUDY DISCONTINUATION AND CLOSURE

The sponsor may choose to temporarily suspend or prematurely terminate study or a study site with or without cause. Written notification, documenting the reason for study suspension or termination, will be provided by the sponsor, as applicable, to the investigator and IRB.

If the study is prematurely terminated or suspended, the Principal Investigator (PI) will promptly inform, as applicable, study participants, the Institutional Review Board (IRB), and sponsor and will provide the reason(s) for the termination or suspension. Study participants will be contacted, as applicable, and be informed of changes to study visit schedule.

Circumstances that may warrant termination or suspension include, but are not limited to:

- Determination of unexpected, significant, or unacceptable risk to participants
- Demonstration of efficacy that would warrant stopping
- Insufficient compliance to protocol requirements
- Data that are not sufficiently complete and/or evaluable
- Determination that the primary endpoint has been met
- Determination of futility

Study and/or study site may resume once concerns about safety, protocol compliance, and data quality are addressed, and satisfy the sponsor, IRB and/or Food and Drug Administration (FDA).

---

### 10.1.3 CONFIDENTIALITY AND PRIVACY

Participant confidentiality and privacy is strictly held in trust by the participating investigators, their staff, and the sponsor(s). This confidentiality is extended to cover the clinical information relating to participants. Therefore, the study protocol, documentation, data, and all other information generated will be held in strict confidence. No information concerning the study or the data will be released to any unauthorized third party without prior written approval of the sponsor.

All research activities will be conducted in as private a setting as possible.

The study monitor, other authorized representatives of the sponsor, representatives of the Institutional Review Board (IRB), regulatory agencies may inspect all documents and records required to be maintained by the investigator, including but not limited to, medical records (office, clinic, or hospital) and pharmacy records for the participants in this study. The clinical study site will permit access to such records.

The study participant's contact information will be securely stored at each clinical site for internal use during the study. At the end of the study, all records will continue to be kept in a secure location for as long a period as dictated by the reviewing IRB, Institutional policies, or sponsor requirements.

Study participant research data, which is for purposes of statistical analysis and scientific reporting, will be transmitted to and stored with the sponsor. This will not include the participant's contact or identifying information. Rather, individual participants and their research data will be identified by a unique study identification number. The study data entry and study management systems used by clinical sites and by Arrinex research staff will be secured and password protected.

---

### 10.1.4 CLINICAL MONITORING

Clinical site monitoring is conducted to ensure that the rights and well-being of trial participants are protected, that the reported trial data are accurate, complete, and verifiable, and that the conduct of the trial is in compliance with the currently approved protocol/amendment(s), with International Conference on Harmonisation Good Clinical Practice (ICH GCP), and with applicable regulatory requirement(s).

A risk-based approach to monitoring will be utilized and details of clinical site monitoring will be documented in a Clinical Monitoring Plan (CMP). The CMP will describe in detail who will conduct the monitoring, at what frequency monitoring will be done, at what level of detail monitoring will be performed, and the distribution of monitoring reports. An increased level of monitoring may be utilized either at an individual site or for the study as a whole in the event of, but not limited to, data quality issues or increased incidence of AEs.

---

#### 10.1.5 QUALITY ASSURANCE AND QUALITY CONTROL

Each clinical site will perform internal quality management of study conduct, data collection, documentation and completion. An individualized quality management plan will be developed to describe a site's quality management.]

Quality control (QC) procedures will be implemented beginning with the data entry system and data QC checks that will be run on the database will be generated. Any missing data or data anomalies will be communicated to the site(s) for clarification/resolution.

Following written Standard Operating Procedures (SOPs), the monitors will verify that the clinical trial is conducted and data are generated and biological specimens are collected, documented (recorded), and reported in compliance with the protocol, International Conference on Harmonisation Good Clinical Practice (ICH GCP), and applicable regulatory requirements (e.g., Good Manufacturing Practices (GMP)).

The investigational site will provide direct access to all trial related sites, source data/documents, and reports for the purpose of monitoring and auditing by the sponsor, and inspection by local and regulatory authorities.

---

#### 10.1.6 DATA HANDLING AND RECORD KEEPING

---

##### 10.1.6.1 DATA COLLECTION AND MANAGEMENT RESPONSIBILITIES

Data collection is the responsibility of the clinical trial staff at the site under the supervision of the site investigator. The investigator is responsible for ensuring the accuracy, completeness, legibility, and timeliness of the data reported.

All source documents should be completed in a neat, legible manner to ensure accurate interpretation of data.

Hardcopies of the study visit worksheets will be provided for use as source document worksheets for recording data for each participant enrolled in the study. Data recorded in the electronic case report form (eCRF) derived from source documents should be consistent with the data recorded on the source documents.

Clinical data (including adverse events (AEs), concomitant medications, and expected adverse reactions data) will be entered into Medrio (<https://medrio.com>), a 21 CFR Part 11-compliant data capture system provided by the Sponsor. The data system includes password protection and internal quality checks, such as automatic range checks, to identify data that appear inconsistent, incomplete, or inaccurate. Clinical data will be entered directly from the source documents.

---

#### 10.1.6.2 STUDY RECORDS RETENTION

Study documents should be retained for a minimum of 2 years after the close-out of the study and until there are no pending or contemplated marketing applications. These documents should be retained for a longer period, however, if required by local regulations. No records will be destroyed without the written consent of the sponsor, if applicable. It is the responsibility of the sponsor to inform the investigator when these documents no longer need to be retained.

---

#### 10.1.7 PROTOCOL DEVIATIONS

A protocol deviation is any noncompliance with the clinical trial protocol, International Conference on Harmonisation Good Clinical Practice (ICH GCP), or Manual of Procedures (MOP) requirements. The noncompliance may be either on the part of the participant, the investigator, or the study site staff. As a result of deviations, corrective actions are to be developed by the site and implemented promptly.

These practices are consistent with ICH GCP:

- 4.5 Compliance with Protocol, sections 4.5.1, 4.5.2, and 4.5.3
- 5.1 Quality Assurance and Quality Control, section 5.1.1
- 5.20 Noncompliance, sections 5.20.1, and 5.20.2.

It is the responsibility of the site investigator to use continuous vigilance to identify and report deviations within five (5) working days of identification of the protocol deviation, or within five (5) working days of the scheduled protocol-required activity. All deviations must be addressed in study source documents, reported to the Sponsor.

Protocol deviations must be sent to the reviewing Institutional Review Board (IRB), when applicable per their policies. The site investigator is responsible for knowing and adhering to the reviewing IRB requirements. Further details about the handling of protocol deviations will be included in the MOP.

---

#### 10.1.8 FINANCIAL DISCLOSURE

Investigators shall provide financial disclosure according to applicable regulations.

